### 13.5.2 Secondary endpoints (patient-reported symptoms and adverse effects)

4. Plasma proteins involved in coagulation: Factors VIII and IX, von Willebrand Factor, total protein S. We expect that these levels will be different between arms, higher Factor VIII activity and Factor IX, von Willebrand Factor levels but lower total Protein S levels in the oral arm
5. Plasma markers of systemic estrogenic effect (IGF-1, IGFBP-3, and SHBG). We expect that these levels will be different between arms, with significant decreases in IGF-1 and increases in IGFBP-3[58] and SHBG in the oral arm but not in the gel arm.
6. Patient reported symptoms (BESS Questionnaire): This is a validated instrument that captures patient reported symptoms in a standard format. These data will be compared across arms as reported previously [59]. We expect that these levels will be different between arms, favoring the gel arm.

### 13.5.3 Exploratory endpoints

7. IHC markers: CD-68 macrophage marker as a surrogate for response to therapy. p16 and COX-2 We expect that changes in these biomarkers will be non-inferior in the gel arm.
8. Plasma levels of steroid hormones (estradiol, progesterone)]. We expect that changes in these biomarkers will be greater in the oral arm.
9. Breast tissue of steroid hormones (estradiol, progesterone) between arms. We expect that changes in these biomarkers will be greater in the oral arm.
10. Fraction of subjects with no residual DCIS in the surgical specimen. We expect that the fraction of subjects with no residual DCIS will be similar in both arms.

### 13.5.4 Analysis Plan for Secondary Endpoints:

Secondary outcomes will be summarized by

treatment arm using descriptive statistics, including mean and confidence interval, or median and interquartile range for continuous outcomes, and proportions and confidence intervals for categorical variables. Outcomes will be compared between arms, with two main types of analyses being conducted: noninferiority testing and testing for differences between arms, depending on the specific hypotheses for each outcome. **Noninferiority analyses.** Similar to the primary outcome, we expect changes in secondary efficacy outcomes (Oncotype DCIS-Score) to be similar (noninferior) in the 4-OHT gel arm vs. oral tamoxifen arm. Because preliminary data necessary for setting noninferiority margins are not available for all endpoints, we will use a strategy similar to how the non-inferiority margin was set for the primary endpoint, i.e. we will set the margin  $M$  to correspond to a 35% change from the average baseline value observed among all patients (i.e. pooling across both study arms). These biomarkers will be compared between arms using ANCOVA models similar to those described for the primary endpoint, with post-treatment measurement as the outcome variable, and with treatment arm and baseline value as predictors, and testing  $H_0: \gamma \geq M$  vs.  $H_1: \gamma < M$  as described above. **Treatment differences.** Continuous endpoints for which treatment differences are expected post-treatment (breast and plasma levels of TAM and its metabolites; plasma proteins involved in coagulation; plasma markers of systemic estrogenic effect; and BESS questionnaire) will be compared between arms using a two-sample t-test. Normality assumption will be checked, and data may be transformed (e.g. logarithmically) to satisfy the normality assumption. If no suitable transformation can be found, groups will be compared using the Wilcoxon ranksum test. Additional exploratory analyses will include linear regression models and will adjust for additional covariates. Outcomes for which changes are expected to be different between arms will be analyzed using ANCOVA models as described for the primary endpoint, but testing whether the treatment effect is 0 rather than the non-inferiority margin  $M$ , i.e.  $H_0: \gamma = 0$  vs.  $H_1: \gamma \neq 0$ . These tests will be two-sided. Tests of these pre-specified hypotheses will not be adjusted for multiple comparisons, and will be interpreted accordingly.

**Adverse Events.** AEs will be assessed using CTCAE. Worst grade toxicity for each AE type will be summarized by arm using descriptive statistics. For each AE type, proportions of patients experiencing toxicity of any grade will be compared between arms using Fisher's exact test.

**Treatment Compliance.** Compliance will be defined as described in Section 5.7. Each patient will be determined as compliant or non-compliant for each treatment component (capsules compliance and gel compliance). Treatment compliance rates based on active ingredient component will be summarized using proportions, and compliance rates will be compared between arms using Fisher's exact test. In addition, in order to determine whether compliance is different for capsule vs. gel administration, within-subject differences in treatment component compliance will be analyzed using the McNemar test among all patients, regardless of treatment arm.

**Subgroup analysis.** Exploratory analyses will be conducted by menopausal status (pre or peri-menopausal vs. post-menopausal). Descriptive statistics will be used to summarize study endpoints by group. In addition, linear regression models as described above will be used with the addition of menopausal status and possibly its interaction with treatment as predictors. Model-based linear contrasts will be constructed to test relevant treatment noninferiority or superiority hypotheses within subgroups. Similar analyses will be conducted in the subgroup of women with invasion in the post-treatment surgical sample.

**13.5.5 Analysis Plan for Exploratory Analyses.** Exploratory endpoints will be analyzed similarly to the primary and secondary endpoint analysis, driven by the hypotheses regarding treatment differences or between arms. In an additional exploratory analysis we will examine correlation between mRNA Ki67 expression and Ki67 IHC staining in a subset of study participants with both assays. Graphical tools will be used and data will be summarized using a correlation coefficient. Linear regression models with ki67 IHC assay as the outcome and mRNA ki67 assay as the predictor may be used to further examine the relationship, e.g. if the association appears nonlinear. Linear mixed effects models may also be used if paired assays are performed at both pre- and post-treatment, and will include subject as the random effect to account for the within-subject correlation between the two time points. This analysis will guide planning of future trials and is not intended as a formal endpoint for the present trial.

**Pathologic response:** Another endpoint of interest is the evaluation of pathologic response, complete (no residual DCIS in the surgical sample). If there is no residual DCIS in the surgical sample, this could mean that the DCIS was small enough at diagnosis that it was ablated by the core needle biopsy; or that the residual DCIS responded completely to therapy. With our present design it is not possible to distinguish between these two possibilities, but we will explore the possibility of pathologic complete response (pCR) in the following ways: the rate of “no residual DCIS” in clinical series and in our institution is about 10%. If we observe that the rate of no residual DCIS is doubled to 20%, we will take this as preliminary evidence of pCR.

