## 13.4 Primary Objective, Endpoint(s) and Analysis Plan

### 13.4.1 Hypothesis and Primary Objective:

We hypothesize that the application of 4-OHT gel to the breast at a dose of 2 mg per breast daily will result in a decrease in the Ki-67 labeling index of DCIS lesions that is comparable to the decrease seen with use of oral TAM. Further, that this will occur with 4-OHT concentrations in the breast that are significantly higher than circulating levels. The primary objective of this study is to demonstrate that topical transdermal 4-OHT is not inferior to oral tamoxifen in decreasing Ki-67 labeling index (LI) of DCIS lesions. In the control (oral TAM) group we expect the mean relative decrease in Ki-67 LI in the surgical specimen to be 50% compared to the diagnostic core biopsy samples after therapy. In the study agent group we will accept a relative mean decrease of at least 35% as evidence of non-inferiority.

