## 13.5 Secondary and Exploratory Objectives and Analysis Plans

### 13.5.1 Secondary endpoints (efficacy)

1. Oncotype DCIS-Score (validated RT-PCR assay for 12 genes). We expect that changes in this Score will be non-inferior in the gel arm.
2. Breast tissue and plasma levels of TAM and its metabolites [N-desmethyl tamoxifen (NDT), (E) and (Z) isomers of 4-hydroxytamoxifen (4-OHT), N- desmethyl-4-hydroxytamoxifen (Endoxifen)]. We expect that plasma levels will be different between arms, with higher levels in the oral arm but tissue levels will be similar between arms.
3. Ki67 LI in terminal duct lobular units, evaluated in the same manner as the primary endpoint (KI67 LI in the DCIS lesions). We expect that reduction in TDLU Ki67 LI will be non-inferior in the gel arm.

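### The 35%-of-baseline margin for secondary and exploratory markers would place a gel with no effect inside the margin for any marker that oral tamoxifen lowers by less than 35%

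*Combined protocol and SAP*

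**What the plan says.** Section 13.4.1 expects a 50% mean relative fall in DCIS Ki-67 on oral tamoxifen and adds: "In the study agent group we will accept a relative mean decrease of at least 35% as evidence of non-inferiority". Section 13.4.2 then uses a margin of 2.6 points, which is 35% of the 7.5% baseline.

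Section 13.5.4 extends that construction. It gives the reason, "Because preliminary data necessary for setting noninferiority margins are not available for all endpoints", and sets M "to correspond to a 35% change from the average baseline value observed among all patients". The model is an ANCOVA "with post-treatment measurement as the outcome variable, and with treatment arm and baseline value as predictors", testing H0: γ ≥ M against H1: γ < M.

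Three groups of endpoints are expected to show non-inferiority:

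- **DCIS Score** (13.5.1): "We expect that changes in this Score will be non-inferior in the gel arm". This is the only marker named in the non-inferiority paragraph of 13.5.4.
- **TDLU Ki-67** (13.5.1): "We expect that reduction in TDLU Ki67 LI will be non-inferior in the gel arm". It is described as "Ki67 LI in terminal duct lobular units, evaluated in the same manner as the primary endpoint".
- **CD-68, p16 and COX-2** (13.5.3): "We expect that changes in these biomarkers will be non-inferior in the gel arm". Section 13.5.5 analyses exploratory endpoints in the same way as the primary and secondary ones.

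The plan gives no expected oral-arm change for any of these markers and no alpha for their non-inferiority tests. There is no untreated arm.

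**The concern.** A non-inferiority margin is meant to be smaller than the effect of the active control, so that a treatment with no effect falls outside it. Here the margin is a fixed share of the marker's baseline level and has no link to how far oral tamoxifen moves that marker. The less tamoxifen moves it, the easier non-inferiority becomes. For a marker that tamoxifen barely changes, an inert gel would pass easily, because the two arms would look alike.

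At stake is how a secondary result is read. A statement that the gel is non-inferior on DCIS Score or TDLU Ki-67 would be taken as support for its biological activity. For a marker with a small oral effect, the test as written cannot give that support.

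**Working it through.** **1. The plan's own figure.** Inputs from 13.4.2: baseline mean 7.5, SD 5.4, correlation 0.5, M = 2.6, 40 per arm, one-sided 0.10.

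- SD of change = √(2 × 5.4² × (1 − 0.5)) = 5.4.
- SE of the difference = 5.4 × √(2/40) = 1.207, and 2.6/1.207 = 2.153.
- Power is 80.5% from the noncentral t with 78 df, or 80.8% by normal approximation. The stated 80.5% reproduces.
- The margin is 0.35 × 7.5 = 2.625, rounded to 2.6. It is not the gap between a 50% and a 35% fall, which is 0.15 × 7.5 = 1.125.

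**2. Where an inert gel lies under the secondary rule.** Let B be the baseline mean, T the oral reduction as a fraction of B, and γ gel minus oral on the post-treatment value, with lower values better and no transformation.

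- Inert gel: post-treatment mean B. Oral: B(1 − T). So γ = T × B.
- The margin is 0.35 × B, so H1 is true exactly when T < 0.35.
- Share of the oral effect retained at the margin = (T − 0.35)/T. This is 30% at T = 0.50 and 0% at T = 0.35. At T = 0.20 a gel that raised the marker by up to 15% of baseline would still be inside.

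**3. Chance that an inert gel is declared non-inferior.** The coefficient of variation (CV) of these markers is not given. I use 0.72 (5.4/7.5, as for DCIS Ki-67) and 0.40 (an assumption with no source in the documents), with correlation 0.5 and 40 per arm. In units of baseline:

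- SE = CV × √(1 − 0.5²) × √(2/40) = 0.139 (CV 0.72) or 0.0775 (CV 0.40).
- P = Φ((0.35 − T)/SE − z), with z = 1.2816 at one-sided 0.10 and 1.960 at 0.025.

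| T | one-sided 0.10, CV 0.72 / 0.40 | one-sided 0.025, CV 0.72 / 0.40 |
|---|---|---|
| 30% | 18% / 26% | 5% / 9% |
| 20% | 42% / 74% | 19% / 49% |
| 10% | 70% / 97% | 43% / 90% |
| 35% | 10% / 10% | 2.5% / 2.5% |

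Comparing change scores instead of using ANCOVA gives lower figures at 0.10: 17-23%, 36-65% and 60-93% at T = 30, 20 and 10.

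**4. TDLU Ki-67.** Its margin could be 2.6 points or 35% of its own baseline. On the first reading, 2.6 points exceeds a full 50% oral effect whenever the TDLU baseline is below 2.6/0.50 = 5.2%. The documents do not give that baseline.

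**The case against.** **The secondary rule copies the primary one.** This stands. A reader might infer that 13.5.4 departs from the primary by turning an acceptable fall into an allowed deficit, but 13.4.2 already does so. Under the primary assumptions the oral arm falls by 3.75 points, so the boundary gel falls by 3.75 − 2.6 = 1.15 points, about 15% of baseline, against the 35% accepted in 13.4.1.

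**Lying inside the margin is not the same as being declared non-inferior.** This also stands. A reader might infer that an inert gel automatically passes, or that no secondary non-inferiority claim can show any gel effect. The documents support neither. At T = 30 the chance is 18-26% at one-sided 0.10 and only 5-9% at 0.025. At T = 50, the only oral effect the plan states (for DCIS Ki-67), an inert gel is outside the margin.

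**The margin is estimated from trial data.** This is true but immaterial. With 80 patients the added SE is 0.35 × CV/√80, or 0.028 at CV 0.72, which raises the SE from 0.139 to 0.142, about 2%.

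**The 2.6-point TDLU margin is only one reading.** This is right. Section 8.2.3 ties TDLU Ki-67 to the primary through its measurement methods, and the 35% rule is written for secondary efficacy outcomes. What stands is that the margin is unclear.

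**These are secondary, unadjusted Phase IIB analyses.** The plan admits that margin data are lacking and will report summaries by arm with confidence intervals. That softens the consequence but does not stop an unsupported claim from following out of the rule as written.

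**A 70% retention test (35/50) is not a clean replacement.** Its SE is CV × √0.75 × √((1 + 0.7²)/40) = 0.120 or 0.0669. If gel equals oral at T = 50, the distance from the null is 0.3 × 0.50 = 0.15, giving about 49% (CV 0.72) to 83% (CV 0.40) power at one-sided 0.10. It would also be stricter than the primary test, so it suits a supportive role only.

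**Conclusion.** The concern holds in a conditional form. For any marker that oral tamoxifen lowers by less than 35% of baseline, the 13.5.4 margin includes a gel with no effect. This follows from the hypotheses alone. The chance of a false claim runs from 5% to 97% over T = 30 to 10. That range rests on assumed variability, correlation and alpha, and on an oral effect the documents do not give, so it is unknown whether any of these markers falls below 35%.

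A reader might go further and infer that the primary conclusion is invalid for the same reason. The documents do not support that: at the expected 50% oral fall, an inert gel differs by 3.75 points and lies outside 2.6. The primary margin shares the rule's origin and needs reconciling with 13.4.1, but this point affects only the secondary and exploratory non-inferiority statements.

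**What to change.** Amend 13.5.4 before unblinding:

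1. Make a non-inferiority statement on DCIS Score, TDLU Ki-67 or an IHC marker only if γ < M is shown and the oral arm's own reduction is shown to exceed M. Together these imply a gel reduction above zero. An inert gel would then meet both conditions with probability no greater than the alpha used for each, whatever T is.
2. Otherwise report the between-arm difference with its confidence interval and make no non-inferiority claim.
3. State the alpha for these tests, and which margin TDLU Ki-67 takes (2.6 points or 35% of its own baseline). State the direction of benefit for CD-68, p16 and COX-2.
4. The 70% retention contrast may be reported as supportive, with its limited power stated.
5. Note that without an untreated arm a change from core biopsy to excision is not purely a drug effect, so the condition on the oral arm is not full proof of assay sensitivity.
6. Reconcile the rule with the primary margin in 13.4.1 and 13.4.2.

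The cost is wording only: no patients, visits or assays. The downside is fewer secondary claims. At T = 50 the oral-arm condition alone would be met with probability Φ(0.15/(CV/√40) − 1.2816), about 51% (CV 0.72) to 86% (CV 0.40) at one-sided 0.10, taking the SD of change as the CV and M as fixed.

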**1.2 Secondary Objectives –**

1. To compare changes from pre-therapy to post-therapy in the Oncotype DCIS-Score between arms (this is a validated RT-PCR assay for 12 genes).
2. To compare between group post-therapy breast tissue and plasma levels of TAM and its metabolites [N-desmethyl tamoxifen (NDT), (E) and (Z) isomers of 4-hydroxytamoxifen (4-OHT), N- desmethyl-4-hydroxytamoxifen (Endoxifen)].
3. To compare the Ki-67 labeling index in the terminal duct lobular units (TDLUs), evaluated in the same manner as the primary endpoint.
4. To compare changes from pre-therapy to post-therapy in plasma proteins involved in coagulation: Factors VIII and IX, von Willebrand Factor, total protein S between arms.
5. To compare changes from pre-therapy to post-therapy in plasma markers of systemic estrogenic effect (IGF-1, IGFBP-3, and SHBG).
6. To compare changes from pre-therapy to post-therapy in symptoms as captured in the Breast Cancer Prevention Trial (BCPT) Eight Symptom Scale (BESS) questionnaire and skin reactions to 4-OHT gel.

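### Coagulation proteins, estrogenic markers and BESS are assigned to a t-test with no baseline term, although baseline is collected and the plan already has an ANCOVA rule that fits

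*Combined protocol and SAP*

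**What the plan says.** The treatment-differences part of section 13.5.4 contains two rules.

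- The first covers "Continuous endpoints for which treatment differences are expected post-treatment". Its named list holds breast and plasma levels of tamoxifen and its metabolites, and then "plasma proteins involved in coagulation; plasma markers of systemic estrogenic effect; and BESS questionnaire) will be compared between arms using a two-sample t-test". No baseline term is mentioned. The fallback, if no transformation works, is the Wilcoxon rank-sum test.
- The second names no endpoint: "Outcomes for which changes are expected to be different between arms will be analyzed using ANCOVA models as described for the primary endpoint", with a two-sided test of a zero treatment effect.

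Between the two stands one further provision: "Additional exploratory analyses will include linear regression models and will adjust for additional covariates".

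Section 1.2 separates the endpoints differently.

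- Objective 2, drug levels, is post-therapy only: "To compare between group post-therapy breast tissue and plasma levels of TAM and its metabolites".
- Objective 4: "To compare changes from pre-therapy to post-therapy in plasma proteins involved in coagulation".
- Objective 5: "To compare changes from pre-therapy to post-therapy in plasma markers of systemic estrogenic effect".
- Objective 6: "To compare changes from pre-therapy to post-therapy in symptoms as captured in the Breast Cancer Prevention Trial" (the BESS questionnaire).

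Section 2.3.3 expects the coagulation and estrogenic markers to change in the oral arm and not in the gel arm. Sections 3.7, 7.1 and 7.2.1 provide baseline BESS, citrate plasma for the coagulation panel, and EDTA plasma for IGF-1, IGFBP-3 and SHBG. Section 13.4.3 recommends ANCOVA for a continuous outcome measured before and after treatment in a randomized trial.

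**The concern.** These endpoints carry the expectation in section 13.1 that the gel is less toxic than oral tamoxifen. Only 80 to 90 women are expected to contribute to them (section 13.2). A comparison that leaves out a baseline value already in the database gives wider intervals than necessary whenever baseline predicts the post-treatment value.

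The plan gives no reason for departing from its own recommendation. The t-test list puts outcomes measured before and after treatment together with drug levels that are compared only after treatment, a distinction the objectives keep.

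A second, smaller issue is that the unnamed ANCOVA rule also fits these endpoints. An analyst could defend either test for the same outcome, and the plan does not say which one leads.

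**Working it through.** **Inputs from the documents.** There are 80 to 90 women for secondary endpoints, or 40 to 45 per arm if split equally (13.2). Secondary tests of difference are two-sided (13.5.4). The only stated pre/post correlation is 0.5, and it is for Ki67 (13.4.2).

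**Assumed.** Two-sided alpha 0.05, a true difference of 0.5 SD, and correlation ρ of 0.3, 0.5 or 0.7 for these endpoints.

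**Check of method on the plan's own figure.** No power is stated for the secondary endpoints, so the primary calculation is used. With SD of change 5.4, margin 2.6, 40 per arm and one-sided alpha 0.10:

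- SD of change = √[2 × 5.4² × (1 − 0.5)] = 5.4
- SE = 5.4 × √(2/40) = 1.207, so the noncentrality is 2.6/1.207 = 2.15
- Noncentral t with 78 df gives 80.5%, which matches section 13.4.2.

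**Post-value t-test, 45 per arm.** SE = √(2/45) = 0.211 SD, and the noncentrality at 0.5 SD is 0.5/0.211 = 2.37. Power is 65.0%, the 95% CI half-width is 0.419 SD, and the difference detectable with 80% power is 0.60 SD.

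**ANCOVA.** Relative to the post-value t-test, variance is multiplied by (1 − ρ²) × [1 + 1/(2n − 4)], and one degree of freedom is lost. The bracket is 1 + 1/86 = 1.012 at 45 per arm.

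| ρ | 1 − ρ² | Power, 45/arm (without bracket) | Power, 40/arm (without bracket) | CI half-width, 45/arm (without bracket) | t-test n/arm for equal precision, 45/(1 − ρ²) |
|---|---|---|---|---|---|
| t-test | 1 | 65.0% | 59.8% | 0.42 SD | 45 |
| 0.3 | 0.91 | 68.6% (69.1%) | 63.3% (63.9%) | 0.40 SD | 49.5 |
| 0.5 | 0.75 | 76.8% (77.3%) | 71.7% (72.2%) | 0.36 SD | 60.0 |
| 0.7 | 0.51 | 90.4% (90.7%) | 86.7% (87.1%) | 0.30 SD | 88.2 |

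A simulation with 20,000 trials per setting at ρ = 0.5 and 45 per arm gave 65.3% against 77.1% power, with type I error 4.8% against 4.7%.

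**Downside.** At ρ = 0, ANCOVA power is 64.5%, a loss of 0.5 points. The standard error breaks even at ρ of about 0.11.

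**Larger effect.** At 0.8 SD and 45 per arm, power is 96.4% for the t-test and 97.6%, 99.1% and 100.0% for ANCOVA (without the bracket), so little is gained.

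**If the t-test was meant on change scores.** The variance of a change is 2(1 − ρ), so the ANCOVA to change-score ratio is (1 − ρ²)/[2(1 − ρ)] = (1 + ρ)/2, or 0.65, 0.75 and 0.85. Change-score power at 45 per arm is 51%, 65% and 86%, still below ANCOVA at each ρ.

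**BESS.** The figures above assume normal data. A simulated 0-to-4 item had 60% zeros, a latent shift of 0.5 SD and 45 per arm, all assumed. t-test power was 54–55%. ANCOVA power was 56%, 62% and 73% at latent ρ of 0.3, 0.5 and 0.7. Type I error was about 5% for both.

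**Choice of test.** If both tests were run and the smaller p-value reported, simulated type I error would be 6.4–8.2% for normal data and 6.0–7.7% for the BESS-like item, instead of 5%. This is a worst case, and the plan does not propose it.

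**The case against.** The strongest reply is that 13.5.4 already contains the remedy. Objectives 4 to 6 are stated as changes, so the ANCOVA sentence can be read as covering them, and the only defect is that two rules overlap. That reading is tenable but is not the natural one. The t-test list names these endpoints, section 13.5.2 speaks of levels, and the ANCOVA sentence has another possible use in the plasma steroid hormones, through sections 13.5.3 and 13.5.5. Under either reading, one main analysis must be named.

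Second, the scale of the t-test is not stated outright, and section 13.4.2 applies a t-test to changes. A change score would use baseline, and the gain at ρ = 0.7 would shrink to 86% against about 90%. At ρ = 0.3 it would grow. ANCOVA is ahead in every case computed.

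Third, the size of the gain is assumed throughout, and it is small for large effects or weak correlation. That stands. So do two small costs: one degree of freedom, and the loss of women without a baseline value from a complete-case model.

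Fourth, section 13.5.2 says BESS will be compared as in an earlier report, which is not available here. Whether that method conflicts with either rule cannot be judged.

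Finally, these are unadjusted secondary endpoints, the t-test is valid, and further regression is planned. Those models are labelled exploratory and do not name baseline, so they mitigate only in part.

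**Conclusion.** The concern holds. The main analysis named for these three endpoint groups leaves out a baseline that is collected, does not match how objectives 4 to 6 are worded, and departs from the plan's own recommendation without a reason.

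The consequence is avoidable imprecision, not bias. At the Ki67 planning correlation of 0.5, borrowed here as an assumption, variance falls by about 25% and the gain equals about 15 more women per arm under the t-test (60 against 45). Over correlations of 0.3 to 0.7 the power gain for a 0.5 SD difference at 45 per arm is roughly 4 to 25 points. It is smaller for a skewed BESS item and small for an effect of 0.8 SD. The true gain is unknown because the documents give no correlation for these endpoints.

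This should be corrected before unblinding. It does not touch the primary conclusion.

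**What to change.** In section 13.5.4:

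- Move Factors VIII and IX, von Willebrand factor, total protein S, IGF-1, IGFBP-3, SHBG and BESS scores from the t-test list to the existing ANCOVA rule. The model is post-treatment value on arm, baseline value and menopausal status, with a two-sided test of a zero arm effect. Name it as the single main analysis.
- Keep the transformation provision, applied to both baseline and post-treatment values. If no transformation is suitable, use a rank-based fallback, preferably one that includes baseline.
- State how women with a missing baseline value are handled.
- For BESS, name the score to be analysed and reconcile the method with the earlier report cited in 13.5.2.
- State that plasma estradiol and progesterone, which have baseline samples, follow the same ANCOVA rule.
- Keep the t-test and Wilcoxon rule for tamoxifen and metabolite levels.

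The cost is SAP wording. No additional patients, samples or visits are needed.
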